### **9.3. Key Secondary Efficacy Estimands and Analyses**

#### **9.3.1. Hierarchical Testing Approach of Key Secondary Efficacy Estimands**

If the superiority of both(one) SEL-212 treatment group(s) against placebo for the main estimand of the primary efficacy is shown with a p-value  $\leq 0.025$ , the hierarchical testing approach will continue to the testing of the main estimands of the key secondary efficacy comparing pairwise both (one) SEL-212 treatments against placebo. Only the main estimands of the key secondary efficacy will be tested in the successive order as defined in Section 6.2. The test result of the  $n^{\text{th}}$  key secondary efficacy estimand will be considered as confirmatory, if the p-value of the two-sided test of the previous estimand resulted in a value less or equal 0.025.

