If the superiority of both (one) SEL-212 treatment group(s) against placebo for the main estimand of the primary efficacy is shown with a p-value \leq 0.025, the hierarchical testing approach will continue to the testing of the main estimands of the key secondary efficacy comparing pairwise both (one) SEL-212 treatments against placebo. Only the main estimands of the key secondary efficacy will be tested in the successive order. The test result of the nth key secondary efficacy estimand will be considered as confirmatory if the p-value of the two-sided test of the previous estimand resulted in a value less or equal 0.025.

Most main estimands with a continuous or numerical endpoint will be tested between each SEL-212 treatment group versus placebo using the mixed model for repeated measures (MMRM) with the change from baseline in the respective variable as dependent variable, and treatment, treatment-by-period interaction, randomization stratum and baseline value of the respective variable as fixed effect variables. The Least Square (LS) Mean difference between each SEL-212 and placebo treatments groups will be estimated on the treatment-by-period interaction with Treatment Period 6, along with its 97.5% confidence interval, and 2-sided p-values.

The main estimands defined for binary or response variables will be tested between each SEL-212 treatment group versus placebo using the Mantel-Haenszel (MH) estimate and test for common risk

difference considering the randomization stratum of tophus presence (yes/no) or Chi-square test with continuity correction (when comparing the subgroup of patients with tophus at Baseline), as appropriate. The difference of proportions between each SEL-212 and placebo treatments groups will be presented along with its 97.5% confidence interval, and 2-sided p-values.

Descriptive summaries will be provided for all endpoints by treatment group and period, if appropriate.

Further Secondary Efficacy Endpoints and Analyses (During the Double-Blind Treatment Period)

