13.4.2 Key Secondary Efficacy

Hierarchical testing of key efficacy:

If the superiority of both (one) SEL-212 treatment group(s) against placebo for the main estimand of the primary efficacy is shown with a p-value ≤ 0.025 , the hierarchical testing approach will continue to the testing of the main estimands of the key secondary efficacy comparing pairwise both (one) SEL-212 treatments against placebo. Only the main estimands of the key secondary efficacy will be tested in the successive order of the key secondary efficacy endpoints listed below. The test result of the nth key secondary efficacy estimand will be considered as confirmatory if the p-value of the two-sided test of the previous estimand resulted in a value less or equal 0.025.

Key secondary efficacy endpoints:

1. Reduction of mean sUA as computed by subtracting the Baseline sUA level from the mean sUA (area under the sUA time curve) during Treatment Period 6
2. Percent reduction of mean sUA as computed by subtracting the Baseline sUA level from the mean sUA (area under the sUA time curve) during Treatment Period 6
3. The change from Baseline to Treatment Period 6 in the physical summary score of the Short Form Health Survey (SF-36)
4. In patients with tophi at Baseline, the percentage of patients with at least PR (as best response) in overall tophus response evaluation until Day 28 of Treatment Period 6
5. The percentage of patients who achieve and maintain reduction of sUA < 6 mg/dL for at least 80% of the time during Treatment Period TP6 by Day 28 in the subset of patients with tophi at baseline
6. The change from Baseline to Treatment Period 6 in number of tender joints
7. The change from Baseline to Treatment Period 6 in the total score of Health Assessment Questionnaire (HAQ-DI)
8. Gout flare incidence during Treatment Periods 1-6
9. Gout flare incidence during Treatment Periods 1-3

The targeted population for all estimands of the key secondary efficacy endpoints numbered as 1, 2, 3, 6, 7, 8 and 9 is the same population as for the primary efficacy. In case of the key secondary efficacy endpoints numbered 4 and 5, the targeted population is additionally restricted to patients with tophi at baseline.

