### **3.5. Determination of Sample Size**

The sample size estimation is performed for the main estimand for the primary efficacy endpoint from V5.0 of the protocol 'percentage of patients who achieve and maintain reduction of sUA < 6 mg/dL for at least 80% of the time during Treatment Period 6 by Day 28' which defined in Section [6.1](#). This estimand considered the following as treatment failures: patients who discontinue study treatment due to lack of efficacy (eg, meeting stopping rule), patients who discontinue study treatment due to treatment-related or non-treatment related AEs, patients who take prohibited medication that lowers sUA, or patients who are lost to follow up or withdraw consent for reasons other than COVID-19.

Based on the Phase 2 (protocol SEL-212/201) results with SEL-212, the responder rate in all randomized and dosed patients is assumed to be 45% in SEL-212. For placebo a responder rate of 5% is assumed. Considering a randomization ratio of 1:1:1 for SEL-212A and SEL-212B against placebo, a statistical power of 90%, a two-sided alpha-level of 2.5% and using the Chi-square test with continuity correction for the 2 pairwise comparisons of each SEL-212 dose group against placebo, 32:32:32 randomized and dosed patients will be required for each treatment group. Considering the potential that some randomized patients will terminate the study early (approx. 8%), the number of the patients required to be randomized and treated in total is 105 (i.e., 35:35:35) to demonstrate efficacy. Randomized but not treated subjects will be replaced. For the sample size estimation, Chi-square test is used instead of the Mantel-Haenszel test, although the randomization will be stratified for tophus presence (yes/no), as there is no valid assumption of the distribution of this stratification variable within the eligible patient population.

From an amendment in version 6.0 of the protocol, the main estimand for the primary efficacy criterion was updated to include patients who present a positive COVID-19 test along with severe or critical symptoms of COVID-19, and patients who missed all assessments of sUA during TP6, as treatment failures. As these are expected to be unrelated to the treatment, then assuming that the number of additional treatment failures to each arm would be roughly equal, the difference in response rates can still be assumed to be 40%, unless the treatment failure rate due to positive COVID-19 tests along with

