## **9.2. Analyses of Primary Efficacy Estimands**

The statistical testing of each SEL-212 treatment group versus placebo in all four estimands will be performed using the Mantel-Haenszel (MH) estimate and test for common risk difference considering the randomization stratum of tophus presence (yes/no) with a two-sided type 1 error rate  $\alpha = 2.5\%$  to adjust for the two comparisons against placebo. Only the test results of the main estimand will be considered as confirmatory.

In addition, a logistic regression model will be fitted, with response as the outcome variable, tophus presence (yes/no) at baseline, treatment group included as covariates.

The analysis of all four estimands will be carried out based on the ITT population, and analyses on the main, second and third estimand will be performed, but the population will be changed to the mITT, the PP and the all randomized set, as opposed to the ITT.

For missing response evaluation data in TP6 (see also Section 9.1) values will be multiple imputed. The logistic method considering the tophus status at baseline and the treatment group will be applied for the multiple imputation.

For the main, second and fourth estimand of primary efficacy, sensitivity analysis will be performed using the tipping-point analysis for binary response, to investigate the sensitivity to departures from missing-at-random (MAR). For patients with missing response status, the underlying response probability will be varied systematically and comprehensively such that, should one exist, a tipping point can be identified where if

This document is confidential.

the probability of being a non-responder in the treatment group is higher than in the placebo group, the statistical significance switches from treatment effect p-value  $<0.025$  to treatment effect p-value  $\geq 0.025$ . For each arm, the following scenarios will be explored, where the true underlying response probability amongst those with missing response status will have the following probabilities:

0.01, 0.11, 0.21, 0.31, 0.41, 0.51, 0.61, 0.71, 0.81, 0.91, 0.99.

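### The key secondary hierarchy is gated only on the immediately preceding p-value and does not state that testing stops at the first failure, so 2.5% per dose is not guaranteed

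*SAP*

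**What the plan says.** Each SEL-212 dose is tested against placebo at two-sided 2.5%, a level chosen "to adjust for the two comparisons against placebo" (SAP 9.2). If the primary is won for a dose, "the hierarchical testing approach will continue to the testing of the main estimands of the key secondary efficacy" (SAP 9.3.1).

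Nine key secondaries follow in this order (protocol 13.4.2; SAP 6.2):

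1. reduction in mean sUA
2. percent reduction in mean sUA
3. SF-36 physical summary score
4. tophus response
5. the primary sUA response in patients with tophi at baseline
6. tender joints
7. HAQ-DI
8. flare incidence, Treatment Periods 1-6
9. flare incidence, Treatment Periods 1-3

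On order, the SAP says: "Only the main estimands of the key secondary efficacy will be tested in the successive order as defined in Section 6.2". On what may be claimed, the protocol begins "The test result of the nth key secondary efficacy estimand will be considered as confirmatory if the p-value", and both documents complete the rule with "if the p-value of the two-sided test of the previous estimand resulted in a value less or equal 0.025". The synopsis carries the same rule.

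Neither document says that the previous result must itself be confirmatory, that all earlier results must have passed, or that testing ends at the first failure. The sentence sets no direction for the key secondaries. Superiority is required only of the primary.

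**The concern.** A fixed sequence can test every step at the full level because a false claim is possible only by passing the first true null it reaches. That protection rests on stopping at the first failure.

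The sentence here makes the licence for step n depend on one p-value, that of step n-1, whether or not step n-1 was itself entitled to a claim. Suppose SF-36 (3) and tophus response (4) both miss, and endpoint 5 gives p ≤ 0.025. Endpoint 5 is then not confirmatory, because step 4 failed. Its p-value nevertheless satisfies the written condition for tender joints (6).

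The results needed for such a claim will exist. SAP 9.3.2.1 to 9.3.2.9 prescribe a test of every key secondary for every dose, with no condition on earlier steps. The sentence in 9.3.1 is the only rule for sorting confirmatory results from the rest. At stake is whether the key secondary claims carry the 2.5% per dose that the plan intends.

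**Working it through.** **Inputs from the documents.** Two-sided α = 0.025 per dose; responder rates 45% and 5%; 90% power; continuity-corrected chi-square; about 8% early termination; 40 per arm finally (SAP 3.5). About 60% of patients have tophi (SAP 3.4).

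**The plan's own figure first.** With z(0.9875) = 2.2414, z(0.90) = 1.2816 and mean rate 0.25:

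- Uncorrected n = [2.2414·√(2·0.25·0.75) + 1.2816·√(0.45·0.55 + 0.05·0.95)]² / 0.40² = (1.3726 + 0.6961)² / 0.16 = 26.7, so 27.
- Corrected n = (26.7/4)·[1 + √(1 + 4/(26.7·0.40))]² = 31.5, so 32.
- 32/0.92 = 34.8, so 35 per arm and 105 in total. Adding 15 gives 120, or 40 per arm.

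The stated 32, 35 and 105 are reproduced.

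**How likely is endpoint 5 to act as a bridge?** It is tested in about 0.60 × 40 = 24 patients per arm. The exact power of the corrected chi-square at 0.025 for 45% v 5% with 24 per arm is 78%. This assumes that the plan's rates carry over to the tophus subset.

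**False-claim rate per dose.** Assumptions: the primary is won, the nine tests are independent, each null endpoint is significant with probability a = 0.025, and each effective endpoint has power 1 unless stated. Two rules are compared by enumerating all 2⁹ reject/not-reject patterns: the written gate (p at step n-1 only) and a strict fixed sequence (all earlier p ≤ 0.025).

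The pattern with 3, 4 and 6 to 9 null and 5 effective can be done by hand:

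- Endpoint 3 follows an effective endpoint 2, so it yields a false claim with probability a.
- If endpoint 5 is significant, endpoints 6 to 9 yield a false claim with probability a + (1-a)(2a² - a³) = 0.0262. The second term is two adjacent nulls among 7, 8 and 9.
- If endpoint 5 is not significant, two adjacent nulls among 6 to 9 are needed: 1 - [(1-a)⁴ + 4a(1-a)³ + 3a²(1-a)²] = 0.0018.
- At power 1 for endpoint 5: 1 - 0.975 × (1 - 0.0262) = 0.0505.
- At power 0.78: 0.7825 × 0.0262 + 0.2175 × 0.0018 = 0.0209, and 1 - 0.975 × (1 - 0.0209) = 0.0454.

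| Endpoints assumed null | Written gate | Strict sequence |
|---|---|---|
| 3 only | 2.5% | 2.5% |
| 6 to 9 | 2.6% | 2.5% |
| 3 to 9 | 2.8% | 2.5% |
| 3, 4, 6 to 9 (5 at 60% power) | 4.1% | 2.5% |
| 3, 4, 6 to 9 (5 at 78% power) | 4.5% | 2.5% |
| 3, 4, 6 to 9 (5 at full power) | 5.1% | 2.5% |
| 3, 6 and 8 | 7.3% | 2.5% |
| 1, 3, 5, 7 and 9 | 11.9% | 2.5% |

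The last two rows are 1 - 0.975³ and 1 - 0.975⁵: every null sits directly behind an effective endpoint.

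**Correlation and both doses.** A simulation of the 78% case (400,000 draws, between-dose correlation 0.5) with endpoint correlation 0.3 to 0.7 gives 4.5% to 4.1% per dose. Over both doses it gives 8.3% to 7.5%, against 4.6 to 4.7% for the strict sequence.

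**Direction.** These rates count significant differences either way. Counting only false claims in favour of SEL-212, the pattern with 3, 4 and 6 to 9 null gives 2.3% (endpoint 5 at 78% power) to 2.6% (full power) per dose. A strict sequence that also requires the right direction gives 1.25%. The ratio is about the same; the absolute rates are about half.

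**The case against.** The strongest reply is that the plan describes an ordinary fixed sequence in loose words. The section is titled as hierarchical testing, entry depends on the primary, and the estimands are taken in a set order. Many readers will apply the rule recursively: step n needs step n-1, which was reached only through step n-2. On that reading 2.5% per dose holds and nothing is inflated. This is probably what was meant, and no text says that testing continues after a failure. A reader might infer that the plan openly allows claims after a failed step. The documents do not support that; what they show is a missing condition.

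A reader might also infer that a failed step stops nothing. That is wrong even on the literal wording: the next claim is blocked, and reopening needs an intervening p ≤ 0.025.

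A third tempting inference is that the error rate simply doubles. It does so only when an effective endpoint lies between null ones. No document says which endpoints are null, and several patterns show little or no inflation. Nor is the 11.9% pattern realistic. It makes mean sUA reduction null and percent reduction effective, and it makes endpoint 5 null although the primary has been won.

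What survives is that setting an order does not set a stop. The one sentence that says which results count as confirmatory omits the stop, while the tests needed to use the omission are all planned.

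**Conclusion.** The point holds as a defect in the wording of the claim rule. As written, the rule does not guarantee 2.5% per dose for the key secondaries.

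The size ranges from none to several-fold. The pattern most relevant to this ordering has endpoint 5 effective while 3, 4 and 6 to 9 are null, and gives 4.5 to 5.1% per dose against 2.5%. These figures rest on assumptions about which endpoints are null, on independence (moderate correlation lowers them slightly), and on endpoint 5's power, taken as 78% or full.

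The primary comparison and its 2.5% level are untouched; it would be wrong to read this as a threat to the primary claim.

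A minor companion point is that the gate is a two-sided p alone, so a key secondary significantly favouring placebo would formally open the next step. For a null endpoint that has probability 1.25%.

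**What to change.** Replace the gate sentence in SAP 9.3.1, protocol 13.4.2 and the protocol synopsis with:

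> Within each dose, the nth key secondary estimand is confirmatory only if the primary and all preceding key secondary estimands for that dose had two-sided p ≤ 0.025 with the estimate favouring SEL-212; confirmatory testing for that dose stops at the first failure.

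This restores 2.5% per dose and closes the direction gap. Tests after a failure can still be reported, labelled as descriptive. The cost is one sentence in three places, with no added patients, data or analyses. If a fixed sequence was always intended, the set of permitted claims does not change. The wording should be settled before unblinding, so that the choice of reading cannot depend on the results.

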#### **9.3.2. Key Secondary Efficacy Analyses**

##### **9.3.2.1. *Reduction of mean sUA as computed by subtracting the Baseline sUA level from the mean sUA during Treatment Period 6***

Both estimands, as well as the estimands where the ITT is replaced by the mITT, all randomized and PP sets, for this key secondary efficacy will be tested between each SEL-212 treatment group versus placebo using an ANCOVA, with reduction of mean sUA at TP6 from baseline as the dependent variable and

This document is confidential.

treatment and randomization stratum as fixed effects, and baseline sUA value as covariates. Missing values of change from baseline will be multiple imputed by using the RPMM method considering tophus status at baseline and treatment group. The Least Square (LS) Mean difference between each SEL-212 and placebo treatments groups will be estimated along with its 97.5% confidence interval, and 2-sided p-values.

The change from baseline in mean sUA across TP6 will be summarized by treatment group on the ITT, mITT, all randomized and PP populations.

**9.3.2.2. *Percent reduction of mean sUA as computed by subtracting the Baseline sUA level from the mean sUA during Treatment Period 6***

Both estimands, as well as the estimands where the ITT is replaced by the mITT, all randomized and PP sets, for this key secondary efficacy will be tested between each SEL-212 treatment group versus placebo using an ANCOVA, with percentage change of mean sUA at TP6 from baseline as the dependent variable, treatment and, randomization stratum as fixed effects, and baseline sUA value as covariates. Missing values of % change from baseline will be multiple imputed by using the RPMM method considering tophus status at baseline and treatment group. The Least Square (LS) Mean difference between each SEL-212 and placebo treatments groups will be estimated along with its 97.5% confidence interval, and 2-sided p-values.

However, residuals from this model will be checked for conformity to normality assumptions. Differences from normality in these residuals will result in the dependent variable being log-transformed and the ANCOVA applied to this outcome, adjusting for the same covariates. This model will then be considered the primary analysis for this estimand.

The percentage change from baseline in mean sUA across TP6 will be summarized by treatment group on the ITT, mITT all randomized and PP populations.

**9.3.2.3. *The change from Baseline to Day 28 Treatment Period 6 in the physical summary score of the Short Form Health Survey 36 (SF-36)***

Both estimands, as well as the estimands where the ITT is replaced by the mITT, all randomized and PP sets, for this key secondary efficacy endpoint will be tested between each SEL-212 treatment group versus placebo using MMRM with change in SF-36 summary score as dependent variable and treatment, period, treatment-by-period interaction, randomization stratum and baseline value of SF-36 summary score as fixed effect variables. The unstructured covariance structure will be used for the MMRM. The LSMean difference between each SEL-212 and placebo treatments groups will be estimated on the treatment-by-period interaction at TP6-Day 28 visit, along with its 97.5% confidence interval, and 2-sided p-values.

A sensitivity analysis will be performed for the main estimand: missing values of SF-36 physical summary score at TP6-D28 will be multiple imputed by using the RPMM method considering tophus status at baseline and treatment group, and the change from baseline to Day 28 of TP6 in SF-36 summary score will be analyzed using an ANCOVA with treatment and randomization stratum as fixed effects and the baseline value of SF-36 summary score as covariate.

The SF-36 summary score at scheduled visits and the change from baseline will be summarized by treatment group and period, on the ITT, mITT, all randomized and PP populations.

The SF-36 is a 36-item scale constructed to survey health status and quality of life ([Ware 1992](#)). The SF-36 assesses 8 health concepts: limitations in physical activities because of health problems; limitations in social activities because of physical or emotional problems; limitations in usual role activities because of

This document is confidential.

physical health problems; bodily pain; general mental health (psychological distress and well-being); limitations in usual role activities because of emotional problems; vitality (energy and fatigue); and general health perceptions. The standard form of the instruments asks for patients to reply to questions according to how they have felt over the previous week.

The SF-36 consists of 8 scaled domain scores with range 0-100 with higher score indicating better health and 2 component scores (physical component and mental component). The 8 domains are:

- Vitality
- Physical functioning
- Bodily Pain
- General Health Perceptions
- Physical Role Functioning
- Emotional Role Functioning
- Social Role Functioning
- Mental Health

**9.3.2.4.** *In patients with tophi at Baseline, the percentage of patients with at least PR (as best response) in overall tophus response evaluation until Day 28 of Treatment Period TP6*

This efficacy endpoint considers the patients with tophi at baseline and compares between each SEL-212 and placebo the percentage of patients with at least PR (as best response) in the overall tophus response evaluation until Day 28 of TP6. The statistical testing of each SEL-212 treatment group versus placebo in both estimands, as well as the estimands where the ITT is replaced by the mITT, all randomized and PP sets, of this key secondary efficacy will be performed using the Chi-square test with continuity correction with a two-sided type 1 error rate  $\alpha = 2.5\%$  to adjust for the two comparisons against placebo. The analysis of the estimands will be carried out based on the ITT population. In the main estimand, patients with missing information on tophus response until Day 28 of TP6 will be multiple imputed using the logistic method considering the treatment group.

Frequency table of tophaceous patients at baseline with best response in the overall tophus evaluation resulting in at least PR / stable disease progressive disease will be provided by treatment group and period on the ITT, mITT, all randomized and PP populations.

The time until the first tophus reduction (i.e. the first time CR or PR is assessed in overall tophus response) will be summarized using descriptive statistics by treatment group for tophaceous patients at baseline in the ITT, mITT, all randomized and PP populations. Tophus photography can be repeated on TP1D0 or until 14 days post TP1D0 if initial images submitted to the Central Reader were not collected per acquisition guidelines.

**9.3.2.5.** *Percentage of patients who achieve and maintain reduction of sUA < 6mg/dL for at least 80% of the time during Treatment Period TP6 in subset of patients with tophi at baseline*

Both estimands, as well as the estimands where the ITT is replaced by the mITT, all randomized and PP sets, for this key secondary endpoint will be analysed in the same way as the primary endpoint, except a Chi-square test with continuity correction will be performed, given only patients with tophus at baseline

This document is confidential.

will be included in the analysis. In addition, the logistic model used to carry out multiple imputation for missing response evaluation data in TP6 will only include the treatment group in the model (and not tophus status at baseline), as only patients with tophus at baseline will be included in the analysis.

